7.2 Statistical analysis

Primary hypothesis

Statistical analyses for the primary hypothesis will follow the intention-to-treat paradigm, which means that all randomized patients with baseline and 72 week liver biopsies will be included in the treatment group to which they were assigned. Any randomized patient who does not have the requisite biopsies will be accounted for and compared by assigned treatment group. Patients not able to be included in the intention-to-treat analyses will be compared to those who are included with respect to demographic and other characteristics.

Since the primary outcome measure, defined in sections 3.4 and 6.1, is a binary indicator of improvement in histologic activity score after 72 weeks of treatment compared to baseline and since the randomization is stratified by clinic and diabetes status, P-values will be derived from the Mantel-Haenszel χ^2 test for stratified 2x2 tables. The proportion of patients improved in the group assigned to obeticholic acid will be compared to the group assigned to placebo and a two-tailed p-value of ≤ 0.05 will be considered statistically significant.

Stratification

Given the randomized design and adequate size planned for the FLINT trial, it is unlikely that confounding of the treatment groups by covariates related to the change in histologic activity score will occur. However, if confounding should occur, multivariate-adjusted logistic regression analyses with histologic improvement as the binary response and treatment group indicator and any suspected confounders as covariates will be carried out to determine the sensitivity of the primary P-value to confounding.

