Follow-up visits: at 2 and 4 weeks and every 12 weeks after randomization throughout the 72-week treatment phase followed by a 96-week visit after 24 weeks of washout period

Randomization: Centrally administered randomization stratified by clinical center, diabetes status, and blocked by calendar time

Statistical analysis: All primary analyses will be on an “intention-to-treat” basis.

The primary analysis is an intention-to-treat analysis in which the proportions of subjects in the active-treatment group (obeticholic acid, 25 mg q.d.) with histological improvement in NAFLD, as defined by the primary outcome measure, is compared with the proportion of subjects in the placebo group in whom there is improvement. The comparison is made with the use of the Mantel–Haenszel chi-square test, stratified according to diabetes status and clinical center. Subjects who do not undergo an end-of-treatment biopsy are classified as not having had improvement.

Vanguard analysis

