- Missing data: 10% will not have 72 week biopsies and will be considered not improved
- Minimum clinically important difference:
 - 50% higher relative rate of improvement in the obeticholic acid group vs. the placebo group
- Assumed response rates:
 - Expected percent with improved NAFLD (defined above) in the placebo group: 39% (based on PIVENS data and 2 to 1 split for patients on vs not on vitamin E at start of trial)
 - Expected percent with improved NAFLD in the obeticholic acid group: 58%

Safety monitoring: NIDDK appointed DSMB will monitor the data for safety and efficacy for outcomes such as hepatotoxicity, pregnancy, and any other outcomes or events identified as safety-related.

1. Hypothesis and principal objective

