7.3 Missing data

The occurrence of missing data in this trial is expected to be low and equally distributed across the treatment groups. We estimate that careful selection of patients during the screening phase and the consent process should result in no more than 10% missing data from patients who drop out before completing the 72 week treatment period. In primary, intention-to-treat analyses, subjects with missing data will be considered unimproved on the primary outcome measure.

The proportions with missing data will be compared across treatment groups using χ^2 tests. If the amount of missing data exceeds 10%, then a variety of sensitivity analyses will be carried out to compare to the primary analysis using all available non-missing data:

- (1) compare pessimistic and optimistic imputations of the missing values,

- (2) correct for missing data using multiple imputation with 10 replicated samples, and
- (3) use mixed random effects logistic or linear regression models, depending on the type of outcome measure.

Sensitivity analyses (2) and (3) assume that the missing data are missing at random (MAR). It is possible that the missing data is not MAR and, therefore, non-ignorable. A few statistical methods are available when there are non-ignorable missing data patterns and these may be employed to assess sensitivity of the results to non-ignorable missing data if the level on the missing data exceeds 10%; however all such methods involve strong assumptions that cannot be verified from the available data.

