7.4 Justification of sample size

A total of 280 patients in 2 groups of equal size (140 per group) will be included to compare the efficacy of obeticholic acid group vs. placebo group with the primary outcome measure of histological improvement in NAS (as defined in sections 3.4 and 6.1). A sample size of 280 patients with 1:1 randomization would provide 90% power to the study hypothesis to detect a significant difference between the two groups with a type I error rate of 0.05. This sample size takes into account that 10% of participants will not have 72 week biopsies and will be considered not improved based upon intention to treat analysis. The sample size estimation is based upon the assumption that the minimum clinically important difference, defined as 50% higher relative rate of improvement in the obeticholic acid group vs. the placebo group, will be expected with the assumed response rates in the placebo group in the placebo group of 39% (based on PIVENS data and 2 to 1 split for patients on vs not on vitamin E at start of trial) versus expected percent with improved NAFLD in the obeticholic acid group to be 58%. This estimate was derived using centrally-read histology data from the PIVENS trial in which 48% of the vitamin E-assigned group and 20% of the placebo-assigned group had the primary outcome similar to that defined for the FLINT trial. Weighting these data by the FLINT investigator's estimate that 2/3 of patients enrolled in the FLINT trial will be taking vitamin E, gives the 39% response rate. These sample size estimations are conservative and would have a minimal likelihood of a type 2 error.

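### Section 7.2 restricts the intention-to-treat primary analysis to patients with both biopsies, while the synopsis, 7.3 and 7.4 keep every randomized patient and count a missing week-72 biopsy as not improved; 7.2 should be aligned.

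*Protocol*

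**What the plan says.** Section 7.2 (Primary hypothesis) spells out intention-to-treat: "all randomized patients with baseline and 72 week liver biopsies will be included in the treatment group to which they were assigned". Randomized patients lacking the required biopsies are to be accounted for and compared by arm. The section then adds: "Patients not able to be included in the intention-to-treat analyses will be compared to those who are included", with respect to demographic and other characteristics. So 7.2 expects some randomized patients to fall outside the analysis that it calls intention-to-treat.

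Four other places give a different rule:

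- Synopsis, Statistical analysis, within the description of the primary analysis: "Subjects who do not undergo an end-of-treatment biopsy are classified as not having had improvement".
- Synopsis, Sample size considerations: "Missing data: 10% will not have 72 week biopsies and will be considered not improved".
- Section 7.3: "In primary, intention-to-treat analyses, subjects with missing data will be considered unimproved on the primary outcome measure".
- Section 7.4: "10% of participants will not have 72 week biopsies and will be considered not improved based upon intention to treat analysis".

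Section 7.3 also makes its sensitivity analyses conditional: "If the amount of missing data exceeds 10%, then a variety of sensitivity analyses will be carried out". It says that these will be "carried out to compare to the primary analysis using all available non-missing data". The protocol does not say which section prevails.

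**The concern.** A baseline biopsy is an entry requirement (section 4.2), so in practice the 7.2 condition removes patients without a week-72 biopsy. Having that biopsy is an event after randomization. If the chance of having it differs between arms for reasons linked to treatment or prognosis, the randomized comparison is no longer protected. The failure rule keeps everyone in the denominator but lowers the response rate in whichever arm loses more biopsies.

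The two rules therefore give different denominators, different estimated response rates and, in some configurations, different conclusions on the primary endpoint. An analyst who programs from 7.2, the section headed Statistical analysis, would produce a completer result under the name intention-to-treat.

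**Working it through.** **1. Inputs from the protocol.** 280 patients, 140 per arm; assumed response 39% on placebo and 58% on obeticholic acid; two-sided alpha 0.05; 90% power; 10% without a week-72 biopsy (synopsis and 7.4). The test is the Mantel-Haenszel chi-square (7.2).

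**2. The plan's own figure.** With pooled variance and no continuity correction,

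n per arm = [1.960·√(2·0.485·0.515) + 1.282·√(0.39·0.61 + 0.58·0.42)]² / 0.19² = (1.385 + 0.889)² / 0.0361 ≈ 144.

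That is 288 in total, against 280 stated. Power with 140 per arm is 89.3%, so 280 is approximately reproduced with all 140 per arm analysed and 39%/58% read as rates among everyone randomized.

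**3. The two rules at the planned 10% missing, balanced.** If 39% and 58% are instead read as rates among patients with a biopsy:

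- 7.2: 126 per arm, 39% vs 58%, difference 19.0 points, power 85.9%.
- Synopsis, 7.3 and 7.4: 140 per arm, 0.9·39% = 35.1% vs 0.9·58% = 52.2%, difference 17.1 points, power 82.6%.

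The protocol does not say which reading of 39%/58% is meant. This step only shows that the two rules target different quantities.

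**4. Illustrative results.** The counts are assumptions. The test is unstratified, so it approximates the planned stratified one. With x improved of n₁ on obeticholic acid, m improved in total and N patients,

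χ² = (x − n₁m/N)² / [n₁n₂m(N−m) / (N²(N−1))].

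| Missing (obeticholic acid / placebo) | Rule | Obeticholic acid vs placebo | χ² | p |
|---|---|---|---|---|
| 14 / 14 | 7.2 | 66/126 vs 49/126 (52.4% vs 38.9%) | 4.60 | 0.032 |
| 14 / 14 | missing = not improved | 66/140 vs 49/140 (47.1% vs 35.0%) | 4.25 | 0.039 |
| 20 / 8 | 7.2 | 66/120 vs 51/132 (55.0% vs 38.6%) | 6.74 | 0.009 |
| 20 / 8 | missing = not improved | 66/140 vs 51/140 (47.1% vs 36.4%) | 3.29 | 0.070 |

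First row in full: N = 252, m = 115, expected 126·115/252 = 57.5, variance 15.69, so χ² = 8.5²/15.69 = 4.60.

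Both scenarios have 28 missing of 280, exactly 10%. Balanced, the rules agree. Unbalanced, they disagree at the two-tailed 0.05 level in 7.2, and equally at the 0.049 that 7.6 sets for the final analysis.

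**5. Close to the planned rates, balanced.** 73/126 vs 49/126 gives p=0.0025 and 73/140 vs 49/140 gives p=0.0039. The conclusion is the same.

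**6. The planned missingness check.** The chi-square comparison in 7.3, applied to 20/140 vs 8/140, gives p=0.017. It would show the imbalance. But 28/280 does not exceed 10%, so the sensitivity analyses would not be required.

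**The case against.** The strongest reply is that the missing-biopsy rule is not really open. It is written four times in advance, once inside the synopsis description of the primary analysis and once under the heading Missing data. Section 7.2 offers no other way to score a missing outcome; it misdescribes who is in the analysis. This stands. A reader might infer that the sponsor is free to choose the denominator after seeing the results, but the documents do not support that: the weight of the text is on one side.

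It does not follow that 7.2 can be left alone. One might read 7.2 as covering patients with data and 7.3 as adding the rest. That reading fails because 7.2 says what intention-to-treat means and names patients outside it. Under the failure rule, nobody would be outside it for want of a week-72 biopsy.

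The closing words of the 7.3 sentence, "carried out to compare to the primary analysis using all available non-missing data", might be taken as a second plain contradiction. They are ambiguous: the reference to non-missing data may describe the primary analysis or the sensitivity analyses, and the paragraph before it states the failure rule. The phrase needs clarifying, no more.

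On size, 7.3 expects missing data to be equally distributed between arms, and under balance the conclusion does not change. Section 5.10 also keeps patients who stop drug for side effects in follow-up, so stopping drug need not mean losing the biopsy. Both points stand, and they make a large imbalance less likely without excluding it.

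Finally, a reader might treat the 10% trigger as part of the same error. It is a separate, openly stated design choice, accompanied by a planned comparison of missingness between arms.

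**Conclusion.** The point holds as an inconsistency in one section. Section 7.2, followed literally, turns the primary analysis into a completer analysis; the synopsis, 7.3 and 7.4 agree with each other on all randomized patients with missing counted as not improved. It needs correcting because it concerns the primary analysis set.

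The numerical effect depends on how missing biopsies divide between arms. At a balanced 10% it is small (p=0.032 vs 0.039 in the illustration). Under the assumed 20/8 split it reverses the conclusion (p=0.009 vs 0.070). A reader might infer from the second pair that the denominator will decide this trial. The documents give no ground for that forecast, because the split and the response counts are assumptions chosen to show sensitivity. All the p-values are unstratified approximations to the planned test.

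**What to change.** - **Section 7.2:** state that all randomized patients are analysed in their assigned group and that those without a week-72 biopsy are counted as not improved.
- **Section 7.2:** delete the sentence on patients who cannot be included in the intention-to-treat analyses. Keep the comparison by arm of patients with and without a week-72 biopsy as description.
- **Both-biopsies analysis:** keep it if wanted, labelled as supportive.
- **Section 7.3:** reword the ambiguous phrase so that the comparator reads *the primary analysis (missing = not improved)*.
- **Optional and secondary:** the 10% trigger looks only at total missingness, so also run the 7.3 sensitivity analyses when missingness differs between arms.

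The first four changes cost a few lines of text; the optional one adds a few tables. Sample size, randomization and visit procedures are unaffected.

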A formal vanguard analysis, marking the end of the vanguard phase of the FLINT trial, will be performed approximately 65 weeks after the first patient is randomized. The analysis will be focused on interim efficacy outcomes and safety information using data from the estimated 25-40% of patients who will have completed at least 24 weeks of follow-up by the time of the interim analysis. Our pre-specified interim criterion for efficacy for continuing the FLINT trial beyond the vanguard phase is based on serum ALT: the criterion for continuation will be considered met if the upper 95% confidence limit on the between-group mean difference in mean changes from baseline to the 24 week measure of ALT, comparing the obeticholic acid versus placebo groups, is at least a 20% net reduction in serum ALT from the overall baseline mean ALT. The analysis will also include detailed safety data, as required by the DSMB, to determine whether any emergent safety issues are present. This vanguard safety analysis will consist of, but is not limited to, counts of adverse events (AEs) and serious adverse events (SAEs) by treatment group with associated P-values based on Fisher's exact tests or other tests, as appropriate. The final decision as to whether to continue the FLINT trial beyond the vanguard phase will be made by the NIDDK program official for the NASH CRN trial, which will be informed by any recommendations from the FLINT DSMB, taking the interim criterion for efficacy, safety, and other relevant information that may arise into account.

Interim analysis

The DSMB will review one planned interim analysis of the primary histological outcome measure. O'Brien-Fleming statistical stopping guidelines for efficacy will be applied. This interim efficacy analysis will occur when approximately 50% (140 of the 280 patients) have completed both baseline and 72 week biopsies. Based on the Lan-DeMets method for group sequential trials using O'Brien-Fleming boundaries (Reboussin et al., 2000), the levels of significance for the interim and final analyses will be $\alpha=0.00305$ and $\alpha=0.049$, respectively.

Sample size considerations

- Total of 280 patients in 2 groups of equal size (140 per group)
- Primary comparison: Obeticholic acid group vs. Placebo group
- Primary outcome measure: Histological improvement in NAFLD (defined above)
- Error protection: Type I = 0.05 and Type II = 0.10 (90% power)

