7.6 Interim analysis

The DSMB will review one planned interim analysis of the primary histological outcome measure. O'Brien-Fleming statistical stopping guidelines for efficacy will be applied. This interim efficacy analysis will occur when approximately 50% (140 of the 280 patients) have completed both baseline and 72 week biopsies. Based on the Lan-DeMets method for group sequential trials using O'Brien-Fleming boundaries,⁹⁶ the levels of significance for the interim and final analyses will be $\alpha=0.00305$ and $\alpha=0.049$, respectively.

Adverse events and other safety measures

The interim analysis will also include detailed safety data, as required by the NIDDK and DSMB, to determine whether any emergent safety issues are present. This interim safety analysis will consist of, but is not limited to, counts of adverse events (AEs) and serious adverse events (SAEs) by treatment group with associated P-values based on Fisher's exact tests or other tests, as appropriate. The final decision as to whether to continue the FLINT trial beyond the vanguard phase will be made by the NIDDK program official for the NASH CRN trial, which will be informed by any recommendations from the FLINT DSMB, taking the interim criterion for efficacy, safety, and other relevant information that may arise into account.

An ongoing assessment of adverse events and other safety measures by the Data and Safety Monitoring Board will determine whether the trial should be continued throughout the duration of the trial including at the interim vanguard analysis time point.

Other interim analyses

An independent Data and Safety Monitoring Board (DSMB), appointed by the NIDDK, will review the protocol for the FLINT trial and monitor the accumulated vanguard, interim, and safety data as the trial progresses to ensure patient safety and to review efficacy. The DSMB is a multidisciplinary group with a written charge provided by the NIDDK. The DSMB reports to the NIDDK, which will in turn, communicate DSMB recommendations to the investigators, as appropriate. The DSMB will hold a meeting to approve the protocol. After the trial commences, the DSMB will meet twice a year to review data and other issues. The DSMB may conduct more frequent meetings if necessary to fulfill its charge. It may also request additional safety reports on a more frequent basis. For example, all serious adverse events are reported to the DSMB for their consideration and recommendations as they occur.

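### Section 7.2 tests the final primary outcome at p ≤ 0.05, but section 7.6 and the synopsis set 0.049 after an efficacy interim; using 0.05 gives 5.10% type I error, not 5%

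*Protocol*

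**What the plan says.** Section 7.2, under the primary hypothesis, compares the proportions improved with a stratified Mantel-Haenszel test and states that "a two-tailed p-value of ≤ 0.05 will be considered statistically significant". It does not mention an interim analysis of this outcome and does not refer to section 7.6.

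Section 7.6 states: "The DSMB will review one planned interim analysis of the primary histological outcome measure". O'Brien-Fleming "statistical stopping guidelines for efficacy will be applied", and the look takes place "when approximately 50% (140 of the 280 patients) have completed both baseline and 72 week biopsies". It then says that "the levels of significance for the interim and final analyses will be" 0.00305 and 0.049 respectively, by the Lan-DeMets method. The synopsis repeats the same look and the same two levels.

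The overall error rate is stated separately. The synopsis gives a type I error of 0.05 and 90% power, and section 7.4 sizes the trial "to detect a significant difference between the two groups with a type I error rate of 0.05".

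**The concern.** An efficacy look that can stop the trial uses up part of the 5% error allowance, so the final test must use slightly less than 0.05. Section 7.6 makes that adjustment and section 7.2 does not. Both sentences are current text and both concern the same two-sided test of the same outcome.

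The 0.05 in section 7.2 cannot be read as the overall error rate, because it is attached to the p-value of the test. If the final p fell above 0.049 and no higher than 0.05, section 7.2 would call the trial positive and section 7.6 would not. Choosing between them after unmasking would be a post hoc decision on whether the trial succeeded.

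**Working it through.** **Inputs.** Final threshold 0.05 (section 7.2). Interim and final levels 0.00305 and 0.049, with the look at 140 of 280 patients, so information fraction t = 0.5 (section 7.6 and synopsis). Overall two-sided type I error 0.05 (synopsis, section 7.4). For power: 140 per group, 39% against 58% (section 7.4).

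**Step 1: reproduce the plan's levels.** The O'Brien-Fleming-type spending function, applied as two symmetric one-sided boundaries of 0.025 each, gives the two-sided interim level

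4 × [1 − Φ(z₀.₉₈₇₅ / √t)] = 4 × [1 − Φ(2.2414 / 0.7071)] = 4 × [1 − Φ(3.1698)] = 4 × 0.000763 = 0.00305.

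This corresponds to |Z₁| ≥ 2.963. Under the null, the interim and final statistics are bivariate normal with correlation √0.5 = 0.707. Solving

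P(|Z₁| ≥ 2.963 or |Z₂| ≥ c) = 0.05

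gives c = 1.969, a nominal two-sided level of 0.0490. Both figures in section 7.6 reproduce. Two other conventions do not match: the spending function applied with α = 0.05 directly gives 0.00557 and 0.0478, and classical O'Brien-Fleming bounds give 0.00517 and 0.0480.

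**Step 2: overall error under each final threshold, after the 0.00305 look at t = 0.5.**

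| Final threshold | Critical value | Overall two-sided type I error |
|---|---|---|
| 0.049 (section 7.6, synopsis) | 1.969 | 0.0500 |
| 0.05 (section 7.2) | 1.960 | 0.0510 |

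A simulation of 20 million null trials gave 0.0500 and 0.0510. The excess is 0.0510 − 0.0500 = 0.0010. This is also the null probability that the trial continues past the look and the two thresholds then disagree: about 1 in 1,000.

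**Step 3: sensitivity to the timing of the look.** The plan says approximately 50%, so I assumed a range of 0.4 to 0.6 and kept the stated levels fixed.

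| t | Final 0.049 | Final 0.05 |
|---|---|---|
| 0.4 | 5.04% | 5.14% |
| 0.5 | 5.00% | 5.10% |
| 0.6 | 4.96% | 5.06% |

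The gap between the columns stays at about 0.1 percentage point.

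**Step 4: cost in power.** For a fixed-design comparison of 39% with 58% at 140 per group, power is 89.3% at a level of 0.05 and 89.2% at 0.049. Before rounding the loss is 0.16 percentage point.

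**The case against.** The strongest reply is that the controlling rule is already in the protocol. The synopsis and section 7.6 both give the method, the timing and the final level of 0.049; that level is correct, and it is the only one tied to the interim. A reader could take section 7.2 as the generic level and section 7.6 as the specific rule for the group-sequential test, and would then reach the right answer. The disagreement is confined to a p-value band 0.001 wide, and sample size, endpoint and conduct are untouched. All of this stands as an argument about weight. It does not remove the conflict, because section 7.2 applies 0.05 to the p-value of the primary test, without qualification, in the section that defines that test.

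Three stronger readings are tempting and are not supported.

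- **A larger inflation, 5.17%.** A reader might count information in biopsies: with 10% missing, 280 × 0.9 = 252 and 140/252 is about 56%. Recomputing the interim level at 56% (0.0055) while leaving the final level at 0.05 gives 5.17%. But section 7.6 itself calls 140 of 280 the 50% point. The synopsis and section 7.3 keep patients without a week-72 biopsy in the analysis as not improved, although one sentence in section 7.2 describes the analysed patients as those with both biopsies. No section prescribes recomputing one level and not the other. The stated 0.00305 at 56%, with 0.05 at the end, gives 5.08%.
- **An error rate that is materially out of control.** The excess is 0.1 percentage point, and it arises only if section 7.2 is followed over section 7.6.
- **Further inflation from the vanguard analysis.** That look uses serum ALT as a rule for continuing the trial. It does not test the histological outcome and adds nothing to this error.

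**Conclusion.** The inconsistency is real and small. As written, section 7.2 sets a final threshold that gives an overall two-sided type I error of 5.10% after the planned look, against the stated 5%; the 0.049 in section 7.6 and the synopsis gives 5.00%. The two differ only for a final p above 0.049 and up to 0.05. The calculation assumes one look at 50% information at 0.00305, stopping if that level is crossed, and the usual normal approximation to the joint distribution of the two test statistics. The point deserves correction because it concerns the success criterion of the only primary test, which should be unambiguous before unmasking. It is not a flaw in the choice of analysis or in the group-sequential design.

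**What to change.** In section 7.2, replace the 0.05 threshold with the final-analysis level from section 7.6 and refer to that section: 0.049 for a look at 50% information. If the look falls at another fraction, use the level given by the Lan-DeMets spending function that section 7.6 already names. The overall two-sided type I error of 0.05 in the synopsis and section 7.4 stays as it is.

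The cost is one sentence, a final threshold 0.001 stricter and less than 0.2 percentage point of power. The sample size does not change.
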